### 6.2.1.2 Recording of Adverse Events

All AEs that occur after the subject has signed consent (regardless of severity and/or perceived relationship to study drug) are to be recorded on the appropriate AE sections (either

'serious' or 'non-serious') in the eCRF. Spontaneously reported SAEs that occur for up to 30 days after the last dose of study drug will also be recorded. The Investigator should complete all the details requested including dates of onset, severity, action taken, outcome, relationship to study drug. Each event should be recorded separately.

### 6.2.1.3 Reporting of Serious Adverse Events

In the case of an SAE (including SUSARs), the Investigator must complete, sign and date the SAE pages from the eCRF, and check that the data are consistent.

Any SAE, including death due to any cause, which occurs during this study, whether or not related to the study drug, must be reported immediately (within 24 hours of the study site's knowledge of the event) by sending a completed, separate SAE Report Form by fax or email to as displayed below::

The report will contain all available information concerning the SAE to enable the Sponsor (or an authorised representative) to file a report, which satisfies regulatory reporting requirements. These timelines apply to initial reports of SAEs and to all follow-up reports.

All SAEs will be recorded on the SAE Report Form, the Adverse Events Form in the eCRF, and source documents. Criteria for documenting the relationship to study drug as well as severity and outcome will be the same as those previously described.

SAEs considered causally related to study treatment that are spontaneously reported to the Investigator more than 30 days after a subject's last dose of study drug should also be collected and reported as described previously, regardless of the time after the trial.

The information must include at least the following:

- Name, address, and telephone number of the reporting Investigator
- Investigational product and study code.
- Subject identification number, sex, and date of birth (recorded as permitted by local authorities).
- Description of the AE, measures taken and outcome.
- Preliminary classification of causal relationship by the Investigator

Additional follow-up information should be completed on an SAE Form with a copy sent to and the original included in the SAE section of the eCRF.

# 6.2.1.4 Reporting of Serious Adverse Events to Regulatory Authorities and Investigators

Investigators will be notified of all SAEs that require prompt submission to their Institutional Review Board (IRB) or Independent Ethics Committee (IEC). Investigators should provide written documentation of IRB/IEC notification for each report to the Sponsor or

will ensure that all applicable SAEs are reported to the appropriate regulatory authorities on behalf of the Sponsor. In countries where the sponsor is responsible for IEC submissions of applicable SAEs, this will be performed by

### 6.2.1.5 Follow-Up of Adverse Events

Any AEs observed from Screening/randomisation up to the final study visit will be followed up to resolution. Resolution means that the subject has returned to a baseline state of health or the Investigator does not expect any further improvement or worsening of the AE.

### 6.2.1.6 Pregnancy

Females of childbearing potential will have a serum pregnancy test performed at Screening and a urine pregnancy test at Day 1 to ensure the exclusion of pregnant women from the study. Female subjects will be instructed to inform the site if they become pregnant during the study. Male subjects will be instructed to inform the site if their partner becomes pregnant during the study.

Female subjects of childbearing potential will have an additional test for pregnancy at Day 42 (the end of the study) and at Day 56 (the Follow-up Visit). In addition, a pregnancy test will be performed at the Early Termination Visit, if a female of childbearing potential discontinues the study prior to Day 42.

Any known or suspected pregnancy that occurs during the study (either in female subjects or female partners of male subjects) must be reported to within 24 hours of the time the Investigator becomes aware of the event, using the Pregnancy Report Form. Suspected pregnancies in subjects will be confirmed with a pregnancy test. Pregnant females will be discontinued from the study.

The Sponsor/designee has a responsibility to monitor the outcome of all pregnancies reported during the study. The Investigator must follow up and document the course and the outcome of all pregnancies even if the subject withdraws consent or the study has finished.

Pregnancy alone is not regarded as an AE unless there is a suspicion that the study drug may have interfered with the effectiveness of contraceptive medications or a suspected AE is associated with pregnancy.

Elective abortions without complications should not be regarded as AEs, unless they were therapeutic abortions (see below). Hospitalisation for normal delivery of a healthy new-born should not be considered an SAE.

All outcomes of pregnancy must be reported by the Investigator to **on** the Pregnancy Outcome Report Form within 30 days after he/she has gained knowledge of the normal delivery or elective abortion. The Investigator must follow up and document the course and the outcome of all pregnancies even if the subject was withdrawn from the study or if the study has finished. The pregnancy will be followed up to delivery; the Investigator must report any complications that occur even though the study has finished.

Any SAE that occurs during pregnancy must be recorded on the SAE Report Form (e.g., maternal serious complications, therapeutic abortion, ectopic pregnancy, stillbirth, neonatal death, congenital anomaly, birth defect) and reported within 24 hours in accordance with the procedure for reporting SAEs (see Section 6.2.1.3).

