# 4.0 INVESTIGATIONAL PLAN

### 4.1 Summary of Study Design

This study will be a multiple-site, double-blind, placebo-controlled, parallel-group proof-of-concept study in approximately 126 subjects with active CD. This study will include subjects who have a confirmed diagnosis of CD for at least three months and have CD involving the ileum and/or colon. Inclusion and exclusion criteria are described in detail in Section 4.4.

The duration of treatment will be 42 days (six weeks); each subject's participation in the study will be approximately 12 weeks. This includes a screening period of up to 28 days, a treatment period of 42 days and a follow-up period of 14 days after the last dose of study drug.

Subjects will be randomised into two treatment arms: either V565 or placebo using a 2:1 active:placebo ratio. Randomisation will be stratified to ensure treatment groups have similar rates of prior anti-TNF $\alpha$  therapy.

Subjects will receive three V565 185 mg capsules three times daily or matching placebo, for 42 days (six weeks). The total daily V565 dose is 1665 mg.

Subjects will be treated with study drug as an add-on to any permitted stable medications already being taken for CD. Permitted CD medications are described in Section 5.10.2. No alteration of background CD medication will be permitted for the duration of the study.

There are six study visits. Two screening visits to assess eligibility will occur during Days - 28 to Day -1; these are Visit 1 (start of screening), and Visit 2 (eligibility ileocolonoscopy). Additional study visits will occur on Day 1 (randomisation and initiation of treatment), Day 14 (Interim Visit), Day 42 (End of Treatment Visit), and Day 56 (Follow up Visit).

Collection of subject-reported variables of the CDAI will be via the diaries given to subjects at Visit 1. Prior to Visit 2, the subject-reported variables will be combined with the variables collected at the site on Visit 1 and the CDAI score will be calculated. In order to have an ileocolonoscopy, eligible subjects must have sufficient diary entries to calculate a CDAI score, a CDAI score  $\geq$ 220 to  $\leq$ 450 and a CRP  $\geq$ 5 mg/L (or if CRP is normal, FCP  $\geq$ 250 µg/g) prior to Visit 2.

A previous ileocolonoscopy conducted within 12 weeks before Visit 1 may be substituted for the Visit 2 ileocolonoscopy provided it is forwarded to the central reader and was performed in such a way as to enable evaluation by the central reader.

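### Protocol 6.2.1.6 ties pregnancy notification and the first 24-hour report to the study period, while required contraception runs to at least 90 days after the last dose

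*Protocol*

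**What the plan says.** Protocol 6.2.1.6 (Pregnancy) uses the study as its time limit four times:

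- Instruction to women: "Female subjects will be instructed to inform the site if they become pregnant during the study".
- Instruction to men: "Male subjects will be instructed to inform the site if their partner becomes pregnant during the study".
- Report within 24 hours of the investigator becoming aware, on the Pregnancy Report Form: "Any known or suspected pregnancy that occurs during the study (either in female subjects or female partners of male subjects) must be reported".
- Sponsor oversight: "The Sponsor/designee has a responsibility to monitor the outcome of all pregnancies reported during the study".

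The same section also contains duties that outlast the study. Course and outcome are to be followed for all pregnancies after the study is over. "All outcomes of pregnancy must be reported by the Investigator", and "the Investigator must report any complications that occur even though the study has finished". Also, "Any SAE that occurs during pregnancy must be recorded on the SAE Report Form", with 24-hour reporting under the procedure in 6.2.1.3.

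Contraception lasts longer than participation. Protocol 6.2.2 and inclusion criterion 11 require it of women of childbearing potential for at least 90 days after the last dose. The abstinence item in 6.2.2 counts that time within the period of risk from study treatment. Section 4.1 gives participation after screening as "a treatment period of 42 days and a follow-up period of 14 days after the last dose of study drug".

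**The concern.** The protocol asks subjects to avoid conception for at least 90 days after dosing and treats that time as part of the risk period. Yet its express request to be told of a pregnancy, and its express first report, stop when the study stops. If contraception fails after that point, nothing in the protocol tells the subject to let the site know.

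This matters because the continuing duties in 6.2.1.6 fall on the investigator and start only once the site has heard of the pregnancy. The last scheduled contact and the last scheduled pregnancy test are at Day 56. An uncomplicated pregnancy conceived after that, or an event that nobody volunteers, could go unrecorded. The stake is the completeness of a small set of safety data.

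**Working it through.** **The plan's own figure.** Section 4.1 gives participation as about 12 weeks: 28 + 42 + 14 = 84 days, and 84/7 = 12.0 weeks. This reproduces, with participation ending at Day 56.

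**Inputs.** Last dose Day 42 (4.2.2). Follow-up visit Day 56 (4.2.3). Contraception to 90 days after the last dose (6.2.2). Spontaneously reported SAEs collected for 30 days after the last dose (4.2.4).

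**Formula.** Conception days without express cover = (last dose day + 90) − day the study ends. For a last dose on Day 42 the contraception period ends on Day 42 + 90 = Day 132.

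The protocol does not define the phrase 'during the study', so three readings are shown:

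| Study taken to end at | Basis | Days without express cover | Share of 90 |
|---|---|---|---|
| Day 56 | 4.1, 4.2.3 | 132 − 56 = 76 | 84% |
| Day 42 | label used in 6.2.1.6 when listing pregnancy tests | 132 − 42 = 90 | 100% |
| Day 72 | if the 30-day SAE period counts as study | 132 − 72 = 60 | 67% |

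**Visit window.** The Day 42 visit may fall on Day 39 to Day 43. If the last dose moves with it and the study still ends at Day 56, the first row becomes 73 to 77 days (81% to 86%).

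**Early stoppers who attend Day 56** (4.2.5 asks for that visit only where possible). Last dose Day 14: 104 − 56 = 48 days (53%). Last dose Day 1: 91 − 56 = 35 days (39%).

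**Men.** Inclusion criterion 11 and the opening text of 6.2.2 count 90 days from the end of the study. Criterion 12 and item 3 of 6.2.2 count 90 days from the last dose. Counted from the end of the study, with the study ending at Day 56, the period runs to 56 + 90 = Day 146. The uncovered part is then 146 − 56 = 90 of 146 − 42 = 104 post-dose days (87%).

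**Expected events.** The documents give neither a contraceptive failure rate nor the number able to conceive or father a child. Assume 42 to 84 of the 84 planned V565 subjects, and 1% to 5% failure per year, over 76 days:

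- 1%: 42 × 0.01 × 76/365 = 0.09; 84 × 0.01 × 76/365 = 0.17.
- 5%: 42 × 0.05 × 76/365 = 0.44; 84 × 0.05 × 76/365 = 0.87.

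The top value is generous. Ages up to 80 are eligible, and women of childbearing potential must use the methods listed in 6.2.2.

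**The case against.** The strongest reply is that 6.2.1.6 already reaches past the study. Investigators must follow every pregnancy, report every outcome and report complications after the study has ended, and SAEs in pregnancy have their own rule. Section 6.2.1.3 adds causally related SAEs at any later time, and 4.5 has withdrawn subjects advised to keep to the contraception restrictions for 90 days. A reader might infer from the limit that pregnancy reporting as a whole stops at Day 56. The documents do not support that, and this part of the reply stands. What remains is that each of these duties needs the site to know of the pregnancy. Advice to continue contraception is not a request to report its failure.

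A reader might also take 76 of 90 as days on which nothing is reportable. That is too strong as well. The limit attaches to when the pregnancy occurs, and the 24-hour clock runs from the investigator's awareness. A conception by Day 56 that is recognised on, say, Day 80 is covered.

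Nor can one say that every SAE in a later pregnancy is reportable whatever its cause. The rule in 6.2.1.6 has no relatedness test of its own, but it sends reports through 6.2.1.3, which beyond 30 days speaks only of causally related SAEs. How the two combine is unclear.

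Finally, the consent form may already give a longer notification window, so a gap in practice is not shown. Likely exposure is also low: section 2.1 reports no detectable V565 in any Phase 1 serum sample, although it was found in the urine of one subject with Crohn's disease.

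**Conclusion.** The point holds as a minor mismatch in the protocol wording. With dosing to Day 42 and the study ending at Day 56, conceptions from Day 57 to Day 132, 76 of the 90 days, have no express instruction to notify and no express first report. The range across readings of the undefined study end is 60 to 90 of 90. The share is smaller for early stoppers who attend Day 56.

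The gap concerns conceptions after the study ends, chiefly uncomplicated pregnancies and events nobody volunteers. On the assumed inputs, fewer than one such conception is expected in the V565 arm. No endpoint, analysis set or randomised comparison is affected. The conclusion rests on the protocol alone and would matter less if the consent form sets a longer window.

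**What to change.** In Protocol 6.2.1.6, replace the study-period limit in both instructions and in the 24-hour report with: *from informed consent until the end of the required contraception period (at least 90 days after the last dose of study drug, or longer where the protocol or local rules require)*. Reword the sponsor's duty so that it monitors the outcome of all reported pregnancies that occur in that window, including those reported after it closes.

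Reconcile the male contraception wording in inclusion criteria 11 and 12 and in 6.2.2 so that one end date applies. Have sites remind subjects at Day 56 or at the Early Termination Visit.

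The cost is a short protocol wording change, carried into the consent form if that uses the narrower window. No visit or test is added. The downside is that the pregnancy reporting route stays open 76 days longer (76/7 = 10.9, about 11 weeks) for a subject dosed to Day 42. For men it is 90 days longer (90/7 = 12.9, about 13 weeks) if the wording that counts from the end of the study is kept.

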### 6.2.2 Contraception

The need to avoid pregnancy and acceptable methods of contraception should be discussed with male subjects and female subjects of childbearing potential prior to the administration of study drug.

Females of childbearing potential must have a negative serum pregnancy test at Visit 1, a negative urine test at Day 1, and agree to use effective contraception from signing informed consent and for at least 90 days after the last dose of study drug. Males who are sexually active with a female partner of childbearing potential must be willing to use effective contraception from signing informed consent and for 90 days after the study.

- Females of childbearing potential include any female who has experienced menarche and who has not undergone successful surgical sterilisation (hysterectomy, bilateral tubal ligation, salpingectomy, or bilateral oophorectomy) or is not postmenopausal. Postmenopausal is defined as no menses for ≥12 months without an alternative medical cause. Females with questionable menopausal history (e.g., irregular menstrual periods and age >40 years) are considered to be of childbearing potential.
- 2. Females of childbearing potential must use acceptable highly effective (according to Clinical Trial Facilitation Group [CTFG] recommendations) methods of birth control in this study. These include:
  - Combined (oestrogen and progestogen containing) hormonal contraception associated with inhibition of ovulation
    - $\circ$  oral
    - o intravaginal
    - o transdermal
  - Progestogen-only hormonal contraception associated with inhibition of ovulation
    - o oral
    - o injectable

VHsquared Ltd Protocol V56502 Drug Name: V565

- o implantable
- Intrauterine device
- Intrauterine hormone-releasing system
- Bilateral tubal occlusion
- Vasectomised partner (provided that partner is the sole sexual partner of the female of childbearing potential trial participant and that the vasectomised partner has received medical assessment of the surgical success.)
- Sexual abstinence must be true sexual abstinence defined as refraining from heterosexual intercourse as part of the preferred and usual lifestyle of the subject. This behavior must cover the entire period of risk associated with the study treatment, which includes at least the time of screening up to at least 90 days after the end of treatment. The reliability of sexual abstinence needs to be evaluated in relation to the duration of the study. Periodic abstinence (e.g., calendar ovulation, symptothermal, post-ovulation methods), declaration of abstinence for the duration of exposure to study drug, and withdrawal are not acceptable methods of contraception.
- 3. Fertile males who are sexually active with a female partner of childbearing potential must agree to use contraception (condom plus spermicide or partner using acceptable highly effective method) from signing informed consent and for 90 days after last dose.
- 4. Fertile males should be instructed that they are not to donate sperm during the study or up to 90 days the last dose of study drug.
- 5. Subjects must follow the strictest applicable local requirement in regards to contraception as specified by the Regulatory Agency or Ethics Committee approving the trial.

### 6.2.3 Clinical Laboratory Evaluations

Blood will be drawn and urine samples will be collected from each subject at each study visit. The clinical laboratory parameters used as screening tests, efficacy outcomes or for safety monitoring are presented in Table 2.

Clinical laboratory tests will be reviewed for results of potential clinical significance throughout the study (see Section 6.2.1 for definition of clinically significant laboratory results). If the Investigator determines a laboratory abnormality to be clinically significant, it is considered a laboratory AE. However, if possible, the underlying condition causing the laboratory abnormality, rather than the abnormality itself, should be reported as the AE. Clinically significant laboratory results will be followed to resolution or until the Investigator considers the abnormality chronic and/or the subject to be stable.

A central laboratory designated by the Sponsor will be used for all laboratory assessments during the trial. Urine pregnancy testing will be done by dipsticks (supplied by the central laboratory).

If an immediate result is required, a sample should be sent to both the local and central laboratory.

Haematology:	Serum Chemistry:	
White blood cell count (differential, percentages and	Sodium	
absolute count)	Potassium	
Haemoglobin	Blood urea nitrogen/Urea	
Haematocrit	Creatinine	
Red blood cell count	Glucose	
Mean corpuscular volume	Calcium	
Mean corpuscular haemoglobin	Phosphorus	
Mean corpuscular haemoglobin concentration	Total protein	
Red cell distribution width	Albumin	
Platelet count	Aspartate aminotransferase	
	Alanine aminotransferase	
Urinalysis:	Total bilirubin	
Colour	Alkaline phosphatase	
Clarity/Appearance		
Specific gravity	Additional Tests (Females of childbearing potential):	
pH	Serum pregnancy test (at Visit 1)	
Protein	Urine pregnancy at Day 1, Day 42 and Day 56	
Blood	If the urine pregnancy test gives equivocal results at	
Glucose	these visits, or is positive, a serum pregnancy test	
Ketones	will be performed to determine if the subject is	
Bilirubin	pregnant.	
Urobilinogen		
Nitrite	Biomarkers	
Leukocyte esterase	C-reactive protein	
Microscopy	Faecal calprotectin	
Additional Tests (Screening only):		
Activated partial thromboplastin time		
Hepatitis B surface antigen		
Hepatitis B surface antibody		
Hepatitis B core total antibody		
Hepatitis C antibody		
C. difficile toxin and presence of other enteric		
pathogens		
QuantiFERON-TB Gold Test		
×		

**Table 2: Clinical Laboratory Testing** 

# 6.3 Vital Signs, Physical Examination and Other Safety Assessments

### 6.3.1 Vital Signs

Vital signs include systolic blood pressure (SBP), diastolic blood pressure (DBP), heart rate (HR), and body temperature. These data will be collected at the visits indicated in .

Blood pressure (measured after at least five minutes in the sitting position) and HR (measured after at least five minutes in the sitting position) will be recorded at every study visit. Automatic or manual devices may be used, but the same device should be used for any given subject throughout the study wherever possible. The same arm should be used for all measurements, if possible. Blood pressure and HR should be measured after the subject has rested (sitting quietly) for at least five minutes, and more than 10 minutes after any blood draw.

Temperature will be measured as per local standard of care.

### 6.3.2 Physical Examination, Height and Weight

A full physical examination will be performed at the time points indicated in . Physical examinations will be performed by a physician. The complete physical examination performed at Visit 1 and Day 42 will include the examination of the following:

- General appearance
- Eyes
- Ears, nose, throat
- Chest/respiratory
- Heart/cardiovascular
- Gastrointestinal/liver musculoskeletal/extremities
- Dermatological/skin
- Thyroid/neck
- Lymph nodes
- Neurological/psychiatric

At other time points (Day 1, Day 14 and Day 56), a brief physical examinations will include assessments of the skin, lungs, cardiovascular system, abdomen (liver and spleen) and other symptom-directed assessments as appropriate.

Weight (without shoes and in normal street clothes) will be measured at each study visit.

Height (without shoes) and body mass index (BMI) will be measured at Baseline.

